13.4. Efficacy and Safety Analyses

13.4.1. Background and Demographic Characteristics

Baseline demographic and background variables will be summarized by treatment group and overall. For categorical variables, frequencies and percentages will be presented. For continuous variables, descriptive statistics including sample size, mean, median, standard deviation, minimum, and maximum will be presented. A pretreatment score is the average of the scores at the Screening and Randomization visits.

13.4.2. Subjects Accountability

All enrolled subjects will be included in a summary of subject accountability for this study. The frequencies and percentages of enrolled subjects, subjects who received each study injection, subjects

who presented at each visit, subjects who discontinued before study completion (including reason for discontinuation), and subjects who completed the study will be presented.

13.4.3. Efficacy Analyses

13.4.3.1. Primary Efficacy Analysis

The primary efficacy analysis will be performed on the WOMAC VAS pain subscore using longitudinal analysis to incorporate information from pain scores assessed at Weeks 1, 2, 4, 6, 8, 10, and 12. A direct likelihood approach as implemented in the SAS MIXED procedure will be used to estimate model parameters designed to reflect group-specific mean values over time. The primary efficacy hypothesis concerns the over a 12-week evaluation period from Week 1 to Week 12, and the group comparison is defined as the average effect over assessments during these weeks. Supporting analyses involve comparisons reflecting group differences at the various study visits, including landmark analysis at Week 12 and early onset of efficacy at Week 1. In all cases, model parameters will be used to determine comparisons for which statistical significance against null zero hypotheses and corresponding 95% confidence intervals will be provided. The basic longitudinal model will be specified as a repeated-measures model that expresses the pain score as a linear function of treatment, time, treatment-by-time interaction, and clinically relevant covariates (pretreatment pain measurement, K-L score, and sex) and a fixed-site effect.

The model is designed to account for correlations among responses over time and to use these correlations to implicitly impute missing values from the non-missing values. The type=UN option in the SAS MIXED procedure will be used to model correlation patterns across time.

13.4.3.2. Secondary Efficacy Analyses

A longitudinal analysis model will be used as described in the primary efficacy analysis for the analysis of WOMAC VAS physical function subscore, WOMAC VAS stiffness subscore, WOMAC VAS total score, PGIC, CGIC, SF-36 scores, weekly average of daily pain scores, and PASE scores.

Continuous responder analysis with WOMAC VAS pain subscore will be performed, and differences between the SI-613 and placebo groups in the percentages of subjects experiencing a >30% or >50% improvement in WOMAC VAS pain subscore will be analyzed with Fisher's exact test. For the analysis of the percentages of OMERACT-OARSI responders, 11,12 differences between the SI-613 and placebo groups in the percentages of positive responders over 12 weeks will be analyzed with generalized estimating equations (GEE) model. For each post-treatment study visit, subjects will be defined as responders or nonresponders based on the OMERACT-OARSI set of criteria. These repeated binary outcomes (responders/nonresponders) will be modeled with GEE, with the relevant pretreatment covariate of pain (average WOMAC VAS pain score from Visits 1 and 2), clinically relevant covariates (K-L score and sex), and a fixed-site effect. A Wald test based on the estimated regression parameter for treatment group assignment will be used for hypothesis testing for this secondary efficacy objective. For the analysis of the percentages of positive responders, subjects who discontinue from the study prior to Week 12 because of either target knee-related AEs or lack of efficacy will be classified as not improved subjects or nonresponders in the efficacy analysis.

For the analysis of the amount of acetaminophen rescue medication consumed for the target knee, the percentages of subjects using rescue medication will be presented. The analysis of the overall use of acetaminophen rescue medication over 12 weeks will be conducted in the analysis of covariance

(ANCOVA) model of the change from baseline of acetaminophen usage. The baseline acetaminophen usage, K-L score and sex will be included as covariates in the ANCOVA model.

Efficacy analyses will be repeated by using entire period from Week 1 to Week 26.

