Following screening, approximately 80 subjects will be randomized in a 1:1 ratio to treatment with SI-613 or placebo. Randomization will be balanced based on baseline WOMAC VAS pain subscore, Kellgren-Lawrence (K-L) score, sex, and investigational site. Screening may occur 1 to 2 weeks prior to injection (Week 0). As part of the eligibility assessments, subjects will complete the WOMAC (with the VAS pain subscore being used as part of the eligibility assessment) and report their pain on a 100-mm VAS after a 50-foot walk test at Screening and at Week 0 prior to injection. Subjects will be randomized to receive an injection every 4 weeks, a total of 3 injections of either 1% SI-613 or placebo and followed up for 26 weeks after randomization. Subjects will have clinic visits at Weeks 0, 1, 2, 4, 6, 8, 10, 12, 18 and 26. Subjects will receive injections at Weeks 0, 4, and 8. Because the SI-613 and placebo preparations might be visually distinguished in the syringe caused by the difference of the viscosity, the injections will be administered by an unblinded injecting physician who is experienced in IA injection of the knee. The unblinded injecting physician will be instructed on how to maintain blinding of other study team members and subjects from the treatment, and will be otherwise uninvolved with conducting the study, including outcome assessment. At all visits, a blinded evaluating physician or a back-up blinded evaluating physician will conduct the assessments. Subjects will report their signs and symptoms of knee OA through the WOMAC at all visits and PGIC at all follow-up visits. Subjects will also complete a daily diary recording their pain on the 11-point Numeric Rating Scale (NRS) before bed each evening. In addition, the SF-36 will be completed at Weeks 0, 4, 8, 12, and 26 and the PASE will be completed at all visits. The physician will complete the CGIC at all follow-up visits and an examination of the target knee at all visits. MRI will be taken at screening, Weeks 12 and 26 to monitor synovial changes of the target knee and assessed by an independent central imaging evaluator. Subjects must switch to using acetaminophen as a rescue pain medication if they are currently using other pain medications. Acetaminophen will be provided, and pill counts will be used to assess consumption between visits.

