10.5. PASE

Subjects will complete the PASE at the indicated visits (Table 2). A sample can be found in Section 19.4.

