13.2. Randomization

Immediately prior to injection at Week 0, subjects who meet all eligibility criteria will be randomized to a treatment group using a 1:1 ratio of SI-613:placebo.

Subjects will be randomized using a dynamic procedure by a minimization protocol, ¹⁰ balancing treatment assignment on K-L score, baseline WOMAC VAS pain score, sex, and investigational site.

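### As written, the longitudinal models for six secondary endpoints adjust for baseline WOMAC pain but not for the endpoint's own baseline; own-baseline adjustment should be stated and those baselines defined.

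*Combined protocol and SAP*

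**What the plan says.** Section 13.4.3.1 models the WOMAC pain score on treatment, time, their interaction, and "clinically relevant covariates (pretreatment pain measurement, K-L score, and sex) and a fixed-site effect".

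Section 13.4.3.2 extends this to the other continuous endpoints: "A longitudinal analysis model will be used as described in the primary efficacy analysis for the analysis of WOMAC VAS physical function subscore". The same sentence covers WOMAC stiffness and total, PGIC, CGIC, SF-36, weekly diary pain and PASE. It names no substitute covariate.

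Two other analyses in Section 13.4.3.2 do spell out their baseline covariate, and they differ:
- OMERACT-OARSI GEE: "with the relevant pretreatment covariate of pain (average WOMAC VAS pain score from Visits 1 and 2".
- Rescue medication: "The baseline acetaminophen usage, K-L score and sex will be included as covariates in the ANCOVA model".

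The general baseline rule is in Section 13.4.1: "A pretreatment score is the average of the scores at the Screening and Randomization visits".

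Allocation is by minimisation, "balancing treatment assignment on K-L score, baseline WOMAC VAS pain score, sex, and investigational site" (Section 13.2).

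On timing, Section 5 says "the SF-36 will be completed at Weeks 0, 4, 8, 12, and 26 and the PASE will be completed at all visits". Section 10.5 says "Subjects will complete the PASE at the indicated visits (Table 2"), and neither Table 2 nor the Screening procedures in Section 7.2.1 list PASE at Screening. The diary is first handed out at Visit 1 and collected at Visit 2 (Sections 7.2.1 and 7.2.2). It has two daily items, worst and average pain (Section 19.5). Section 4.2 does not say which one forms the weekly average.

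**The concern.** In the primary model the pain covariate is the response's own pretreatment value. Once the response becomes physical function, SF-36 or PASE, the same covariate is another variable's baseline. A programmer who follows the text would fit a model that runs without error but omits what is usually the strongest single predictor of the endpoint.

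Two things follow. The treatment estimate is less precise than the collected data allow. And a chance difference between arms in, say, baseline function stays in the estimate, because minimisation balances baseline WOMAC pain and not function, SF-36 or PASE. With about 40 subjects per arm such differences are not rare. Secondary endpoints are each tested at the two-sided 5% level with no multiplicity adjustment (Sections 13.5.1 and 13.5.4), so it also helps to leave no covariate or diary-item choice open until the data are seen.

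**Working it through.** **The plan's own figure.** Section 13.1 assumes a true difference of 7.5 mm, SD 23 mm and 40 per group, and states an 80% probability of observing at least 3 mm. SE = 23 × √(2/40) = 5.143; Φ((7.5 − 3)/5.143) = Φ(0.875) = 0.809. This reproduces. It concerns the primary endpoint and does not depend on the secondary covariates.

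**Which endpoints are affected, and what baseline each has**

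| Endpoint | Pre-injection data | What is open |
|---|---|---|
| WOMAC function, stiffness, total | Visits 1 and 2 | Covariate wording only; Section 13.4.1 supplies the baseline |
| SF-36 | Visit 2 only | Covariate; the two-visit average does not apply, and one value is available |
| PASE | Visit 2 only under Table 2; Section 5 says all visits | Covariate; reconcile the schedule wording |
| Weekly diary pain | Daily entries between Visits 1 and 2 | Covariate, averaging window, and worst or average item |
| PGIC, CGIC | None (ratings of change since study start) | Nothing; no own baseline exists |

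**Size of the precision loss.** The documents give no correlations, so every value here is an assumption. Let ρ be the correlation of own baseline with the post-treatment average and c the correlation of baseline pain with own baseline. Suppose pain predicts the endpoint only through own baseline, so its correlation with the outcome is cρ.

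- Residual variance with pain alone: 1 − c²ρ².
- Residual variance with pain and own baseline: 1 − ρ². Under this assumption pain adds nothing once own baseline is in the model, so adding own baseline and replacing pain by it give the same value.
- Variance ratio = (1 − c²ρ²)/(1 − ρ²); SE reduction = 1 − 1/√ratio.

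At ρ = 0.5:

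| Endpoint group | Assumed c | Ratio | SE reduction |
|---|---|---|---|
| PASE, SF-36 | 0.40 | (1 − 0.04)/0.75 = 1.280 | 11.6% |
| Function, stiffness | 0.70 | (1 − 0.1225)/0.75 = 1.170 | 7.5% |
| Total, diary pain | 0.85 | (1 − 0.1806)/0.75 = 1.0925 | 4.3% |

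If change rather than score is the response, with equal variances, the ratio is 1 + (1 − ρ)(1 − c²)/(1 + ρ). At ρ = 0.5 this gives the same three values.

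Range for ρ from 0.3 to 0.7, with c from 0.3 to 0.5, 0.6 to 0.8 and 0.8 to 0.9 in the three groups:
- Score modelled: 3.5% to 27%, 1.7% to 21%, and 0.9% to 14%.
- Change modelled: 6.0% to 18%, 3.0% to 14%, and 1.6% to 8.5%.

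**Check by simulation.** With complete data, 40 per arm and 8,000 runs, own baseline in place of pain gave SE reductions of 11.9%, 7.6% and 4.5% at the three table settings. Mean estimates under a zero effect were within 0.004 SD of zero with either covariate, so neither model is biased.

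**Cost of one more covariate.** Eighty subjects less two arms and three covariates leave 75 residual degrees of freedom before site terms (the number of sites is not given). Estimating one more coefficient raises the variance by about 1/75 = 1.3%, or about 0.7% in SE. That offsets most of the gain at the bottom of the score range (0.9%) and little of it at ρ = 0.5.

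**Chance imbalance.** The SD of the between-arm difference in a baseline unrelated to the minimisation factors is √(2/40) = 0.224 SD. If pain is balanced exactly, it falls to 0.224 × √(1 − c²), which is 0.205 at c = 0.4. Unadjusted, a one-SD imbalance of that size moves the estimate by 0.5 × 0.205 = 0.10 SD at ρ = 0.5.

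**The case against.** The strongest reply is that the literal reading is selective. The primary model has the pain score as response and Weeks 1, 2, 4, 6, 8, 10 and 12 as its time points. Neither can carry over to SF-36, which is collected after injection only at Weeks 4, 8, 12 and 26. The reference to the primary model must therefore mean its structure with endpoint-specific inputs, and its pain covariate is the response's own baseline. Section 5 also describes the WOMAC secondary analyses as changes. The GEE is weak evidence the other way, since a composite responder has no baseline of its own.

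Much of this stands, and own-baseline substitution is a plausible intent. It does not close the gap. The response and visits have to be adapted for the model to run at all; the pain covariate does not. It can also be read as deliberate adjustment for a minimisation factor. Section 5 calls the primary endpoint a change too, although Section 13.4.3.1 models the score. Section 13.3 refers to a statistical analysis plan for the definition of major deviations. No separate SAP text was available, so whether it settles the covariate cannot be checked.

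Two further objections are right and shape the fix. Replacing pain by own baseline would drop one of the four minimisation factors when own baseline can simply be added. And the precision figures rest wholly on assumed correlations and on pain acting only through own baseline. If own baseline predicts little beyond pain, the gain is near zero.

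A reader might also infer that no baseline exists for SF-36 and PASE. The documents do not support that: Table 2 leaves one pre-injection value for each. Only the diary baseline is truly undefined.

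**Conclusion.** A minor gap in specification, limited to secondary endpoints. No section states own-baseline adjustment for the six models. Following the text as written would give less precise estimates and leave chance imbalance in those baselines unadjusted.

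The size is illustrative: an SE about 4% to 12% smaller at an assumed own-baseline correlation of 0.5, less about 0.7% for the extra covariate. The gain is near zero under less favourable correlations, and zero if own baseline is already intended.

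Two stronger readings should be avoided. One is that the secondary comparisons are biased. They are not, because baseline is independent of randomised treatment whichever covariate is used. The other is that the authors chose to leave own baseline out. The wording is silent on this and the intent cannot be recovered from it. The primary analysis and the sample-size statement are unaffected either way.

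**What to change.** In Section 13.4.3.2, state that the longitudinal models for WOMAC function, stiffness and total, SF-36, weekly diary pain and PASE include the endpoint's own pretreatment score as a covariate, in addition to pretreatment WOMAC pain, K-L score, sex and site. Define that score as follows:

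- **WOMAC function, stiffness, total:** mean of Visits 1 and 2.
- **SF-36 and PASE:** the Visit 2 pre-injection value, as in Table 2. Reconcile the Section 5 wording on PASE visits with Table 2.
- **Diary pain:** a prespecified average of pre-injection entries between Visits 1 and 2, on the same item (worst or average) that forms the weekly endpoint. Name the item and the averaging window.

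For PGIC and CGIC, which have no baseline, keep WOMAC pain as the only baseline outcome covariate.

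The cost is a few sentences and one degree of freedom per model. All the data are already collected, so no visits, assessments or subjects are added. If own-baseline adjustment was intended all along, the text only needs to say so, and to say whether WOMAC pain stays in the model.

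### The OMERACT-OARSI responder GEE names no visit term, so if response changes over visits and unimputed exits differ by arm, visit mix enters the treatment odds ratio (small effect, nearly free to fix)

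*Combined protocol and SAP*

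**What the plan says.** All of this is in the protocol's statistics section.

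- **Outcome (13.4.3.2).** "For each post-treatment study visit, subjects will be defined as responders or nonresponders based on the OMERACT-OARSI set of criteria". The comparison concerns responders over the whole period: "percentages of positive responders over 12 weeks will be analyzed with generalized estimating equations (GEE) model".
- **Visits.** The primary analysis in 13.4.3.1 uses "pain scores assessed at Weeks 1, 2, 4, 6, 8, 10, and 12", so the responder analysis over the same 12 weeks pools seven visits.
- **Terms in the GEE (13.4.3.2).** Pretreatment pain comes first ("These repeated binary outcomes (responders/nonresponders) will be modeled with GEE, with the relevant pretreatment covariate of pain"). The list then closes and the text goes straight to the test: "clinically relevant covariates (K-L score and sex), and a fixed-site effect. A Wald test".
- **Test (13.4.3.2).** "A Wald test based on the estimated regression parameter for treatment group assignment will be used for hypothesis testing". The working correlation is not stated.
- **Contrast (13.4.3.1).** The primary model "expresses the pain score as a linear function of treatment, time, treatment-by-time interaction", with similar covariates and a site effect. Section 13.4.3.2 extends that model to the continuous secondary scores but gives the GEE its own list.
- **Exits (13.4.3.2 and 13.5.2).** Subjects who discontinue for target knee AEs or lack of efficacy become nonresponders. Section 6.3 lists further routes out, such as the subject's own request, loss to follow-up, non-compliance and site technical problems. No imputation rule for the responder analysis covers these.
- **Repeat (13.4.3.2).** Efficacy analyses are run again over Weeks 1 to 26.

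**The concern.** Fitted as listed, the model gives each arm one response level for the whole of Weeks 1 to 12, given the covariates. A subject who leaves after Week 2 for an uncovered reason supplies two early outcomes and nothing later. If early and late response differ, and one arm has more such subjects, that arm's pooled rate leans towards the early level even when the drug does nothing. The single treatment parameter then carries follow-up length as well as treatment effect.

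This happens even when the exits are unrelated to the subject's own response. In that setting a visit effect would remove the shift. At stake is the accuracy of one reported secondary odds ratio; the primary analysis already models time.

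**Working it through.** **Design figure.** The only calculated figure in the plan is in 13.1: 80% probability of observing a difference of at least 3 mm, with 40 per arm, true difference 7.5 mm and SD 23 mm. SE = 23 × √(2/40) = 5.143, and Φ((7.5 − 3)/5.143) = Φ(0.875) = 80.9%. It reproduces. There is no design figure for the responder endpoint.

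**Inputs.** From the plan: seven visits, 1:1 allocation, 40 per arm, two-sided 5%. Assumed, because the plan gives none: response curves, exit rates, timing of exits, and within-subject correlation. Odds ratios below are the arm with fewer exits against the arm with more, with no true effect. Only exits outside the nonresponder rule are counted unless stated.

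**Step 1: independence working correlation.** Take response 25, 30, 35, 40, 45, 50, 55% over the seven visits in both arms, with exits after the second visit. With no visit term and no other covariates, the fitted rate for exit fraction d is

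p(d) = [0.25 + 0.30 + (1 − d)(0.35 + 0.40 + 0.45 + 0.50 + 0.55)] / [2 + 5(1 − d)] = [0.55 + 2.25(1 − d)] / [2 + 5(1 − d)]

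- d = 10%: 2.575/6.5 = 0.3962
- d = 20%: 2.35/6 = 0.3917
- d = 30%: 2.125/5.5 = 0.3864

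For 20% v 10%, OR = (0.3962/0.6038)/(0.3917/0.6083) = 1.019. For 30% v 10%, OR = 1.042. The differences are 0.45 and 0.98 percentage points.

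**Step 2: exchangeable working correlation.** A subject with m visits now has total weight m/(1 + (m − 1)ρ). A latent correlation of 0.5 gives a binary correlation of about (2/π)arcsin(0.5) = 1/3. Early leavers (m = 2, mean response 0.275) weigh 2/1.333 = 1.5. Completers (m = 7, mean 0.40) weigh 7/3 = 2.333. Each visit of an early leaver therefore counts 0.75, against 0.333 for a completer.

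- d = 10%: (0.15 × 0.275 + 2.1 × 0.40)/2.25 = 0.3917
- d = 20%: (0.3 × 0.275 + 1.867 × 0.40)/2.167 = 0.3827
- d = 30%: (0.45 × 0.275 + 1.633 × 0.40)/2.083 = 0.3730

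The ORs are 1.039 (20% v 10%) and 1.082 (30% v 10%), about twice the shift on the log scale. Simulated GEE with 400 per arm gave 1/0.960 = 1.042 and 1/0.916 = 1.092. With visit as a factor, simulated ORs lay between 0.98 and 1.02 in every scenario.

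**Step 3: other response shapes (independence, 30% v 10%).**

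| Assumed response, first to last visit | OR |
|---|---|
| Flat 40% | 1.000 |
| Rising 35% to 50% | 1/0.980 = 1.020 |
| Rising 15% to 60% | 1/0.938 = 1.066 |
| Falling 55% to 40% | 1/1.020 = 0.980 |

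**Step 4: wider range of exits.** Logistic GEE, 80 subjects, response rising from 25% to 58%, exits after one to four visits, 600-900 runs per scenario, no true effect:

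| Exits | OR, exchangeable | OR, independence |
|---|---|---|
| 15% v 5% | 1.05 | 1.02 |
| 20% v 10% | 1.05 | 1.02 |
| 25% v 10% | 1.07-1.08 | 1.04 |
| 35% v 10% | 1.14 | 1.07 |

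With visit as a factor the OR was 1.00-1.01. With equal exits there was no bias. Power at an assumed effect was 41-43% either way. A further simulation of the same setting, comparing the two models on the same data, gave smaller log-OR shifts: 0.035 (15% v 5%) to 0.089 (35% v 10%) under exchangeable, and 0.018 to 0.058 under independence.

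**Step 5: the nonresponder rule.** On the Step 1 curve at 20% v 10%, if every exit is coded nonresponder the denominator is 7 in both arms. The difference is then 2.35/7 − 2.575/7 = −3.21 points with or without a visit term. If half are so coded, it is −1.99 points without visit and −1.88 with it.

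**Step 6: effect on the test.** With 40 per arm the SD of the log OR was 0.29-0.33. A bias of 0.045 is 0.045/0.3 = 0.15 SD, and rejection becomes Φ(−1.96 + 0.15) + Φ(−1.96 − 0.15) = 5.3%. The largest bias, 0.128, is 0.43 SD and gives 7.1%. Simulated rejection was 4.0-7.0% without visit and 3.7-6.2% with it (400 runs; Monte Carlo error √(0.05 × 0.95/400) = 1.1 points). One of the 7.0% results had a mean log OR of only −0.022, too small to explain it, so these rates do not separate the two models.

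**The case against.** **The conditions are not in the plan.** The documents give no responder rates by visit, no rising trend and no expected exit rate. A reader might infer that the arm losing more subjects early will look worse. The documents do not support that: flat response or equal exits give no shift, and falling response reverses it. This stands, so the point is conditional. On the other side, 13.4.3.1 itself models time and separates Week 1 onset from the Week 12 landmark, so the plan does not treat response as constant for pain.

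**The nonresponder rule covers the exits most likely to depend on treatment.** This also stands: Step 5 shows that a visit term does nothing for those subjects. Only the remaining exits matter, and nothing in the documents says they will differ by arm in a blinded, randomised trial.

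**The list may be incomplete wording.** Treatment does not appear in the covariate sentence either; it appears only in the sentence on the Wald test. Section 13.3 also refers to a statistical analysis plan for some detail, and only protocol text was available here. So a deliberate decision to assume constant response cannot be inferred. Even so, the two readings give different estimates, and the choice should be written down before unblinding.

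**The size is small and the endpoint is secondary.** This stands. Against it, 13.1 sizes the study on the observed effect and not on significance, so an avoidable bias in an estimate is worth removing when it costs almost nothing.

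**Conclusion.** The point holds as a minor, conditional one. The GEE as written names no visit term while pooling seven visits. If response changes over those visits and exits outside the nonresponder rule differ by arm, the treatment odds ratio absorbs part of the visit effect.

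Under an assumed rise from 25% to 58% and exits of 15-35% v 5-10%, the spurious OR is about 1.02 to 1.14. The upper end needs both an exchangeable working correlation and 14 v 4 of 40 subjects leaving within four visits for uncovered reasons (35% and 10% of 40). The log-OR bias, roughly 0.02 to 0.13, is small beside an SD of about 0.3.

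A reader might go further and conclude that the Wald test is invalid. The calculations do not show that: no clear type I error inflation appears at moderate imbalance, and only the most extreme case approaches 7%. The primary analysis is unaffected.

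All of this assumes exits unrelated to the subject's response. Where exits depend on response in ways the model does not capture, a visit term alone does not remove the bias.

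**What to change.** In 13.4.3.2, before unblinding:

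1. Add visit as a categorical effect to the OMERACT-OARSI GEE and list treatment explicitly among the model terms. Keep the single treatment parameter and its Wald test.
2. Name the working correlation, since it roughly doubles or halves any shift.
3. Do the same for the Week 1-26 repeat, which adds Weeks 18 and 26, well after the last injection at Week 8. A constant response level is harder to defend there.
4. Optionally, show a treatment-by-visit version as support, to match the primary model.

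The cost is six degrees of freedom for seven visits (eight for the nine visits to Week 26), no new data, and no loss of power in the simulations.

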5. INVESTIGATIONAL PLAN

This is a phase 2, multicenter, randomized, double-blind, placebo-controlled study to evaluate the efficacy and safety of a 3 mL IA knee injection of 30 mg SI-613 given every 4 weeks for the treatment of OA knee pain over 12 weeks. The subject will be followed up for 26 weeks after randomization.

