13. STATISTICS

13.1. Power and Sample Size Determination

Approximately 80 subjects with symptomatic primary OA of the knee will be randomized. Forty subjects per group (80 total subjects) were calculated to provide an 80% probability that a 3 mm (or greater) treatment difference point effect for the primary endpoint will be observed, but not necessarily at a statistically significant level. This assumes that the true treatment difference is 7.5 mm and standard deviation is 23 mm based on the previous Japanese 613/1022 study.

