13.5. Other Statistical Considerations

13.5.1. Significance Levels

The type I error rate will be set at the 5% significance level for the primary efficacy analysis.

All secondary and exploratory efficacy analyses will be performed at the 2-sided 5% significance level.

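### The OMERACT-OARSI responder test names no small-sample correction and no rule for small sites; with the usual robust GEE variance, about 80 subjects and fixed site effects, its error rate would exceed the nominal 5%

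*Combined protocol and SAP*

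**What the plan says.** - **Model (13.4.3.2).** Each subject is classed as responder or nonresponder at each post-treatment visit. "These repeated binary outcomes (responders/nonresponders) will be modeled with GEE", with pretreatment WOMAC pain, then "clinically relevant covariates (K-L score and sex), and a fixed-site effect".
- **Test (13.4.3.2).** "A Wald test based on the estimated regression parameter for treatment group assignment will be used for hypothesis testing".
- **Level (13.5.1).** "All secondary and exploratory efficacy analyses will be performed at the 2-sided 5% significance level". Section 13.5.4 applies no multiplicity adjustment to the efficacy analyses.
- **Size (5).** "approximately 80 subjects will be randomized in a 1:1 ratio to treatment with SI-613 or placebo". The trial is described as multicenter, but the number of sites is not stated.
- **Not stated for this model.** The text gives no link function, working correlation, variance estimator, reference distribution or small-sample correction. It also has no rule for small sites, sites without variation in response, or non-convergence.

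**The concern.** The independent units in this analysis are the subjects, about 80. The seven visits through Week 12 add correlated rows, not further units. The usual robust (sandwich) variance is biased downward when the number of subject-level parameters is not small relative to the number of subjects, and every fixed site term adds a parameter. Comparing the resulting Wald statistic with a normal distribution then rejects too often and gives confidence intervals that are too narrow.

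Fixed site terms raise a second difficulty with binary data. If every response at a site is positive, or every one negative, that site's coefficient has no finite estimate (separation) and a plain fit may not converge. Without a rule set in advance, the analyst would have to choose a remedy after seeing the data.

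At stake are the p-value and interval for one named secondary objective (section 4.2), whose only error control is its own nominal 5%. Section 13.4.3.2 also repeats the efficacy analyses through Week 26, so the weakness carries over to that repeat.

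**Working it through.** **1. The plan's own figure.** Section 13.1 states: "Forty subjects per group (80 total subjects) were calculated to provide an 80% probability that a 3 mm (or greater) treatment difference point effect", assuming that "the true treatment difference is 7.5 mm and standard deviation is 23 mm". The standard error is 23 × √(2/40) = 5.143 mm, and Φ((7.5 − 3)/5.143) = Φ(0.875) = 80.9%. Exactly 80% needs 37.0 per arm. The figure reproduces. It concerns a point estimate for the primary endpoint and sets no error rate for the responder test.

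**2. Inputs.** From the documents: 80 subjects, 1:1 allocation; 7 visits (Weeks 1, 2, 4, 6, 8, 10, 12); minimization on K-L score, baseline pain, sex and site; two-sided 5%. Assumed, because not given: 2 to 16 sites, of equal or uneven size; responder rate 0.3 or 0.5; latent within-subject correlation 0.6 (0.3 and 0.85 in a few settings); 10% dropout; logistic link; exchangeable working correlation. Visit terms were included, although the GEE text does not list them.

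**3. Rough hand check.** With S sites there are p = 5 + (S − 1) subject-level parameters (intercept, treatment, pain, K-L, sex, S − 1 site terms). If the sandwich variance is low by a factor of about 1 − p/80, the rejection rate at 1.96 is 2 × Φ(−1.96 × √(1 − p/80)).

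- S = 2, p = 6: 2 × Φ(−1.885) = 5.9%
- S = 8, p = 12: 2 × Φ(−1.807) = 7.1%
- S = 10, p = 14: 2 × Φ(−1.780) = 7.5%
- S = 16, p = 20: 2 × Φ(−1.697) = 9.0%

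**4. Simulation under no treatment effect** (2,500 trials per setting). Separated sites were set aside before fitting. The corrected test here is Mancl-DeRouen with a t reference on 80 − p degrees of freedom, less any subjects and parameters set aside.

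| Sites | Robust Wald z | Mancl-DeRouen t | Trials with a separated site, equal sizes | Same, uneven sizes |
|---|---|---|---|---|
| 2 | 5.6–6.1% | 3.2–4.0% | 0% | 0.2% |
| 4 | 6.2–7.0% | 3.6–4.3% | 0% | 2.2–3.7% |
| 6 | 5.9–7.8% | 3.3–4.3% | 0% | 7.1–13.8% |
| 8 | 6.4–7.9% | 2.6–3.4% | 0–0.6% | 15.5–27.6% |
| 10 | 7.6–9.3% | 2.7–4.0% | 0–2.5% | 25.8–42.6% |
| 16 | 8.8–10.6% | 2.0–3.0% | 2.6–25.8% | 60.5–77.5% |

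The Monte Carlo standard error is about √(0.07 × 0.93/2500) = 0.5 point. At 2 sites no single setting is far from 5%, but the four average (5.6 + 6.0 + 5.6 + 6.1)/4 = 5.8%, with a standard error under a true 5% of √(0.05 × 0.95/10000) = 0.22 point.

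Plain fits failed in essentially the trials that had a separated site. With those sites set aside, the treatment effect could not be estimated in at most 1.2% of trials.

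**5. Other assumptions.** A second simulation used 20,000 trials per setting, complete data, an independence working correlation and uneven sites. It gave 6.6 / 7.2 / 7.8 / 8.9% for 5 / 8 / 10 / 16 sites, with fitting failures in 0.6 / 4.5 / 9.5 / 37% of trials. A third, with 4,000 trials per setting and 4 to 16 sites, gave 6.7–9.2%.

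**6. Kauermann-Carroll with a t reference.** In the third simulation, with site kept and separated sites set aside, it gave 4.7–5.3%. In the second it gave 4.8 / 4.4 / 4.1% for 5 / 8 / 10 sites but 2.0% at 16, where single-subject sites break the correction. This is why pooling is needed alongside it.

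**The case against.** The strongest reply is that the plan is under-specified rather than wrong. A reader might infer that it prescribes a logistic GEE with an uncorrected sandwich variance. The text names neither the link nor the variance, and a Wald test on the treatment coefficient is compatible with a bias-corrected variance and a t reference. Section 13.3 also leaves the definition of major deviations to a statistical analysis plan, and no separate SAP text is in the document, so fuller detail on this model may exist there. This stands: the inflation is conditional on the usual default being used.

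A reader might also infer that the model often cannot be fitted. The documents do not support that, since they give neither the number nor the sizes of sites. With equal sites, separation is rare up to about 10 sites. It concerns the site terms, not the treatment coefficient, which can nearly always still be estimated. What stands is the narrower point that no rule exists for the case where it occurs.

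Finally, the consequence is small. This is one of many secondary endpoints, tested without multiplicity control, in a phase 2 trial sized for an observed difference rather than for significance. No stated decision depends on this p-value. This also stands, and it limits the severity. It does not remove the point, because every simulated setting for the uncorrected test lay above 5%, and the remedy is a sentence of specification.

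**Conclusion.** The concern holds in conditional form, as a minor point. With the usual robust variance and a normal reference, the responder test would run at roughly 5.6–10.6% instead of 5% for 2 to 16 assumed sites. The unknown number of sites changes the size of the excess but not its direction. No single true error rate can be stated, because site number, site sizes, responder rate and within-subject correlation are not in the documents. A narrower band such as 6.6–8.9% describes one set of assumptions only.

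Non-convergence is a risk if sites are small or uneven, not an expected outcome. The primary analysis is a separate model and is not touched.

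**What to change.** In section 13.4.3.2:

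1. State that the Wald test of treatment uses a bias-corrected sandwich variance (for example Kauermann-Carroll) with a t reference, with degrees of freedom equal to subjects minus parameters. Name the link and working correlation in the same sentence.
2. Keep site in the model. It is a minimization factor (section 13.2) and is in the primary model (section 13.4.3.1).
3. Add a rule, fixed before unblinding, for pooling small sites and sites where all or none of the responses are positive. The rule should also say what is done if the model still does not converge.

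The cost is SAP wording and a procedure option. Confidence intervals for this one secondary endpoint become slightly wider. If many very small sites are left unpooled, the corrected test becomes conservative (2.0% in one simulation at 16 sites), so items 1 and 3 belong together.
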